Staging of Superficial Esophageal Adenocarcinoma using Volumetric Laser Endomicroscopy

March 12, 2021

Principal Investigator:

[name].
Barrett's Esophagus Unit
Division of Gastroenterology and Hepatology
Mayo Clinic
[name]
Email: [contact]
[contact]

Research Preceptor:

[name] MD
[name] Professor of Gastroenterology
Barrett's Esophagus Unit
Division of Gastroenterology and Hepatology
Mayo Clinic
[name]
Email: [contact]
[contact]

A. Background, Innovation and Significance:

The prognosis and management of esophageal adenocarcinoma (EAC) is strongly associated with the stage of disease. Accurate staging is particularly important for superficial EAC given that T1a disease can be treated effectively with endoscopic therapy while T1b disease generally requires esophagectomy due to a higher risk of lymph node metastasis.¹ Our current practice relies on histologic assessment of endoscopic mucosal resection (EMR) specimens to determine depth of invasion. Endoscopic resection and in particular endoscopic submucosal dissection may place patients with T1b disease at an unnecessary risk. Complications such as bleeding have been reported in up to 33%, perforation in up to 5% and esophageal stenosis in up to 30% of patients undergoing resection.² Furthermore, up to 15% of patients who undergo EMR will eventually require surgery.² Volumetric laser endomicroscopy (VLE) is an imaging platform that uses infrared light to generate cross-sectional views of the human esophagus with microscopic resolution.³ VLE has been used to detect dysplasia associated with Barrett's esophagus (BE) but its use in cancer staging has not been previously explored.^{4, 5} We propose that VLE can accurately and comprehensively stage T1 EAC. The use of this technology may help select patients with invasive disease for esophagectomy while avoiding complications associated with endoscopic resection.

B. Specific Aims:

Accurate staging of superficial EAC (T1a vs. T1b) is critical in guiding treatment of early luminal cancer. We hypothesize that VLE can accurately and comprehensively stage T1 EAC. Thus the specific aims of this proposal are:

1. To correlate depth of cancer invasion measured using VLE to depth of invasion established by EMR (clinical gold-standard) in a retrospective cohort of T1 EAC patients.
2. To determine the diagnostic performance of VLE in staging T1 EAC in a prospective cohort of patients undergoing endoscopic evaluation.

C. Technology Review:

The VLE imaging system (Nine Point Medical, MA) consists of an imaging console, monitor and optical probe. The system's optical probe is centered by a balloon (diameter: 14 mm, 17 mm, 20 mm; length: 6 cm) that is deployed through a gastroscope's instrument channel. Imaging is performed by automatic helical pullback of the probe from the distal to the proximal end of the balloon over 90 seconds. A total of 1200 single cross-sectional frames are generated per scan. VLE images have an axial resolution of 7 μ m and can reach an imaging depth of up to 3 mm, providing surface and subsurface microstructural detail. These characteristics make VLE an ideal imaging modality for staging T1 EAC.

The latest generation of VLE platform allows users to identify a region of interest and perform laser-markings that appear as superficial cauterization marks under white-light endoscopy. The advantages of this approach are the ability to perform direct VLE to histology correlation and to demarcate an area for endoscopic resection. Imaging enhancing software provides an en-face VLE view, where anatomical landmarks can be easily identified. This software also superimposes signal

[figure not shown]

Figure 1: (A) Cross-sectional view of esophagus using VLE in patient with non-dysplastic BE (B) Three-dimensional rendering of VLE scan, (C) En-face view of VLE scan with labeled anatomical landmarks. (D) En-face view of VLE scan of patient with T1 EAC with image enhancing software. Area of increased signal intensity demarcated by laser markings corresponding to area of neoplasia. Gastric epithelium shows normal increased signal intensity.

intensity attenuation measurements allowing for recognition of areas of concern and quantification of degree of signal intensity.

A recent advancement in the field of volumetric laser endomicroscopy (VLE) is the release of an FDA approved image enhancement software termed Intelligent real-time image segmentation (IRIS) (Nine Point Medical, Bedford, MA). IRIS highlights established VLE features using a color-graded scale superimposed over cross-sectional and reconstructed en-face views. VLE IRIS features include (1) surface hyper-reflectivity, a pink graded color scale at the epithelial surface that represents the degree of signal decay over depth (signal attenuation), (2) hypo-reflective structures (epithelial glands), filled by a solid blue color and (3) lack of layered architecture represented by an orange graded color bar at the external rim of the VLE image. Our VLE console was recently upgraded with the IRIS software package. Following the study methodology of this IRB protocol we plan to use IRIS to locate and delineate neoplastic regions prior to biopsy or resection. This is a continuum of our work using a previous offline version of IRIS to measure VLE signal attenuation to determine stage (T1a vs T1b) of early esophageal adenocarcinoma. (Endosc Int Open. 2019 Apr;7(4):E462-E470) The use of IRIS is meant to facilitate VLE interpretation and does not impact patient care. VLE scans will be reviewed with and without IRIS enhancement.

D. Research Strategy:

a. Rationale:

We propose that the use of an advanced endoscopic imaging technology designed to image the esophagus in cross-section at microscopic resolution can accurately predict depth of invasion in patients with T1 EAC. An advantage of cancer staging using VLE is that it could prevent unnecessary endoscopic resection and associated complications. This technology also provides comprehensive assessment of the esophagus as compared to the current standard of practice that relies on a discrete area chosen for endoscopic resection to determine depth of invasion.

[figure not shown]
b. Preliminary Data and Published Data:

Our group has performed extensive work aimed at understanding the VLE features associated with BE dysplasia. These features include effacement of layered architecture, atypical gland conformations and increased epithelial (surface) VLE signal intensity.^{4, 5} More recently we validated a computer algorithm that performs segmentation and reconstruction of a VLE scan into an en-face view with superimposed signal intensity profiles. (Figure 1) VLE signal decay is dependent upon several tissue optical characteristics.⁶ This algorithm can be applied to estimate the depth of invasion based on degree of signal attenuation. Figure 2 highlights an example of how depth of invasion can be correlated with VLE signal attenuation. We also reported on the use of this technology to detect subquamous esophageal adenocarcinoma.⁷

Our group has also performed work on histologic determinants of mortality for patients with T1 EAC and described that evidence of lymphovascular invasion and deep margin involvement are significantly associated with reduced overall survival.⁸ Ultimately, the data obtained from the present study will help determine if histologic features such as lymphovascular invasion can also be quantified with VLE.

c. Study Design:

I. Aim1: VLE to histology correlation of T1 EAC depth of invasion

Endoscopic Mucosal Resection Database: Our group has developed a platform for imaging EMR specimens using VLE.⁴ Patients with BE undergo endoscopic EMR after participating in informed consent (IRB).

[figure not shown]

Figure 2: (A) endoscopic mucosal resection specimen of patient with T1a EAC and imaged with (B) VLE (C) Depth of invasion estimated by signal attenuation decay at 340 μm.

ID:12-006665). The fresh EMR specimen is imaged with VLE and inked for orientation. Through an established pathology core lab protocol (Proc 053417.002) for sectioning of the EMR specimens we are able to obtain direct imaging-to- histology correlation Using this imaging platform we have imaged over 200 EMR specimens since 2012 of which 60 specimens were obtained from patients with T1 EAC (T1a EAC, N=45; T1b EAC, N=15).

b. **Histopathologic Review:** EMR histology will be reviewed systematically to assess grade of tumor differentiation, depth of invasion, and presence or absence of lymphovascular invasion. Depth of invasion will be manually quantified by

measuring distance (μm) from mucosal surface to deepest point of invasion. (**Figure 3**) The Paris classification suggests a cut-off of 500 μm to divide depth of submucosal invasion into superficial (sm1) and deep (sm2). This classification has been correlated to depth of invasion defined by layer involvement: (1) **T1a EAC**: tumor invasion into the lamina propria or muscularis mucosa and (2) **T1b EAC**: tumor invading into the submucosa.⁹

c. **Correlation of VLE Signal Attenuation to Depth of Cancer Invasion:** A validated computer algorithm will be used to quantify the degree of signal attenuation in the T1 EAC EMR specimen database identified above. VLE signal attenuation measurements will be correlated to depth of invasion as determined by histology (dB/ μm). Based on these measurements, a cutoff signal attenuation value will be established to distinguish between superficial and deep invasion.

II. Aim 2: Diagnostic performance of VLE in staging T1 EAC

Patient Selection:

a. Patients referred to our institution for management of BE and early neoplasia will be prospectively enrolled in this study. Inclusion criteria include patients with T1 EAC who are undergoing endoscopic evaluation including EMR.

Inclusion:

- Patient over the age of 18
- Patient undergoing an upper endoscopy with prior-biopsy confirmed Barrett's Esophagus.
- Ability to provide written, informed consent
- No significant esophagitis (LA grade <B, C, and D)

Figure 4: Study flow diagram

Exclusion:

- Patients who have achieved complete remission of intestinal metaplasia (CR-IM)
- Patients without visible BE at the time of study EGD
- Patients for whom use of the NvisionVLE device would be in conflict with the instruction for use.
- Prior esophageal or gastric surgical resection
- Significant esophageal stricture requiring dilatation
- Patients who require anticoagulation for who biopsy would be contraindicated
- Patients who are known to be pregnant

b. Endoscopic Evaluation: Patients will undergo high-definition white light endoscopy/narrow band imaging with detailed inspection of the BE mucosa. The length of the BE segment will be measured using Prague criteria (circumferential length, maximal length). Area(s) of mucosal nodularity/irregularity will be classified (Paris classification) and their location recorded (o'clock position, distance from incisors). If clinically indicated, an area(s) will be chosen for EMR.

Figure4:Studyflow diagram

d. Volumetric Laser Endomicroscopy: A VLE

Figure 4: Study flow diagram scan will be performed. The VLE scan will be systematically reviewed based on a previously established protocol. If an area(s) is chosen for EMR during

endoscopic evaluation it will be identified and demarcated using VLE laser markings. If additional areas of concern are identified under VLE, they will be demarcated using VLE laser marking. All area(s) demarcated with VLE but not identified on endoscopic evaluation will undergo targeted biopsies. Area(s) identified under endoscopic evaluation and demarcated with VLE will undergo EMR as outlined below. Standard surveillance biopsies will be obtained across the remaining BE segment.

e. Assessment of Cancer Depth of Invasion: VLE scans will be analyzed using an automated computer algorithm to measure degree of signal attenuation over areas demarcated for EMR. The signal attenuation cut-off established from *aim1* will be used to classify cancers as superficial vs. deep. EMR specimens will be reviewed for grade of tumor differentiation, depth of invasion, and presence or absence of lymphovascular invasion. Depth of tumor invasion will be measured as outlined above and used to classify cancers as superficial vs. deep.

f. Statistical Considerations and Data Analysis: This is a prospective cohort pilot study to determine the diagnostic performance of VLE in staging T1 EAC. To achieve a specificity of 90% with a 95% confidence interval, we estimate that a total of 60 patients with T1 EAC will need to be enrolled in this study taking into account that approximately 75% of patients will be staged as having T1a disease on histology. Sensitivity, specificity, negative predictive value, positive predictive value and diagnostic accuracy will be calculated for VLE compared to histology as the gold-standard in staging T1 EAC. Kappa statistics will be performed to test for agreement of the diagnostic methods.

Anticipated Results, Interpretation and Potential Pitfalls:

In the first aim of this study we explore the correlation between VLE signal attenuation and depth of cancer invasion. We use VLE scans from an EMR database of T1 EAC patients obtained using a validated ex-vivo imaging platform. A novel computer algorithm is used to measure the degree of signal attenuation. We anticipate establishing a cut-off of signal attenuation value that correlates with histologic depth of cancer invasion (superficial vs. deep). A potential setback to this approach is the ability to accurately measure absolute histologic depth of invasion, especially in cases with duplicated muscularis mucosa. This setback is mitigated by our prior experience with histological assessment of EMR specimens in which we established a standardized approach to specimen review that will involve two independent gastrointestinal pathologists.

In the second aim of this study we validate the accuracy of VLE in staging T1 EAC compared to a histologic gold-standard. We anticipate that VLE will be able to distinguish between superficial and deep cancer with a >90% accuracy. A potential pitfall to this approach is that the signal attenuation cut-off will be established by imaging of EMR specimens. There is little variation in imaging characteristics between ex-vivo and in-vivo VLE imaging. However, if we find a broad distribution of signal attenuation measurement in EMR specimens we plan to perform preliminary validation of this approach using a cohort of T1 EAC patients (N=10) who have undergone in-vivo VLE and EMR as part of a previous research protocol.

References:

4. Leggett CL, Gorospe EC, Chan DK, et al. Comparative diagnostic performance of volumetric laser

endomicroscopy and confocal laser endomicroscopy in the detection of dysplasia associated with Barrett's esophagus. *Gastrointest Endosc* 2016;83:880-888 e2.

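### Does the silence on IRIS in the Aim 2 procedure and analysis text put the staging result at risk?

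*Combined protocol and SAP*

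**What the plan says.** All eight mentions of IRIS are in section C. It is described there as software that colours established VLE features on the cross-sectional and en-face views. For this study, "we plan to use IRIS to locate and delineate neoplastic regions prior to biopsy or resection". The section links this to earlier work "using a previous offline version of IRIS to measure VLE signal attenuation to determine stage (T1a vs T1b) of early esophageal adenocarcinoma", and adds that "The use of IRIS is meant to facilitate VLE interpretation and does not impact patient care" and that "VLE scans will be reviewed with and without IRIS enhancement". Earlier in the same section, image-enhancing software is said to overlay signal "intensity attenuation measurements allowing for recognition of areas of concern and quantification of degree of signal intensity".

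Section D.b describes, by function, a validated algorithm that rebuilds a scan as an en-face view with signal profiles and can estimate depth of invasion from attenuation. Aim 1 (D.c.I.c) then states: "A validated computer algorithm will be used to quantify the degree of signal attenuation in the T1 EAC EMR specimen database".

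For Aim 2, section D.c.II.d says "The VLE scan will be systematically reviewed based on a previously established protocol"; that protocol is not reproduced. It also says "All area(s) demarcated with VLE but not identified on endoscopic evaluation will undergo targeted biopsies". Section D.c.II.e measures attenuation by an automated algorithm over the areas marked for EMR and applies the Aim 1 cut-off. Section D.c.II.f plans one set of accuracy measures for VLE against histology, plus kappa.

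**The concern.** Three things look open.

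- **Two reads without a plan.** If the reads with and without IRIS were to be compared, a plain read by someone who has already seen the overlay would not show what VLE does alone. The order could not be repaired later for that reader.
- **Unnamed measuring software.** Aim 2 borrows a numerical cut-off from Aim 1, so both aims need the same measurement. The algorithm is called validated in one place, automated in another and novel in a third. An earlier version of IRIS once did this job, and the console has since been upgraded. A changed tool could make the cut-off wrong for Aim 2.
- **Patient care.** IRIS is said not to affect care, yet it is used to find regions before biopsy, and areas marked on VLE alone are biopsied.

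At stake would be whether the reported sensitivity and specificity belong to one well-defined test.

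**Working it through.** **Planning figure.** The inputs, all from D.c.II.f, are specificity 90%, a 95% interval, about 75% T1a and 60 patients.

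- T1a patients: 60 × 0.75 = 45. T1b patients: 60 × 0.25 = 15.
- Wald half-width at 45: 1.96 × √(0.90 × 0.10 / 45) = 1.96 × 0.0447 = 0.088, or 8.8 points.
- In reverse, a half-width of 8.77 points needs 45 T1a patients, and 45 / 0.75 = 60.

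The plan states no half-width, so 8.8 points is back-solved. IRIS is not an input at any step, and clarifying its use would move none of these numbers. The rest of the check is a comparison of texts.

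**Is a with/without comparison part of the plan?** Section B lists two aims: correlating VLE depth with EMR depth, and the diagnostic performance of VLE in staging. Neither concerns IRIS. Section D.c.II.f compares VLE with histology only, and its kappa reads most naturally as agreement between those two. The promise of two reads therefore feeds no listed result. How reviewers work through a scan is delegated to a protocol that is not in the document.

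**Is the measuring tool undefined?** Read in order, the text is fairly continuous. D.b describes a validated algorithm that estimates depth from attenuation. D.c.I.c uses a validated algorithm to set the cut-off. D.c.II.e uses an automated algorithm and applies that cut-off. One algorithm across both aims is the natural reading. Section C presents console IRIS mainly as a display. A name and version are missing, as is a sentence tying the console upgrade to the measurement or separating it.

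**Could IRIS reach the staging table another way?** Yes, through the region measured. Attenuation is taken over areas marked for EMR, and IRIS may help outline them. So it cannot be said that the reads have no bearing on the automated call. However, section D.c.II.b has EMR areas chosen at endoscopic evaluation, which is described before the VLE scan. Outlining with IRIS would then be part of the VLE test as used, and the accuracy estimate would describe that test.

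**Does the biopsy rule reach the staging table?** Areas found on VLE alone go to targeted biopsy. Section D.c.II.e takes depth from EMR specimens and attenuation from EMR areas. On that text, the VLE-only areas do not enter the T1a/T1b comparison.

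**The case for a change.** The best case for a change is that section C describes planned use under this protocol, not background, and so D.c.II should carry it through. Read order cannot be recovered afterwards for a reader who has seen the overlay. The measured region is part of the index test and IRIS may shape it. A cut-off is only as good as the sameness of the measurement behind it, and the Anticipated Results section discusses only the difference between ex-vivo and in-vivo imaging, not software version.

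Part of this stands. A cross-reference and a software name and version would help the reader. The statement that IRIS leaves care untouched also sits uneasily with its use before biopsy and with the rule for VLE-only areas. Those statements must be reconciled, although care may there mean treatment decisions only.

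What does not stand is the step from silence to a faulty result. The argument on read order applies only if a comparison is to be reported, and none is listed. Setting an order now would cost endoscopy time, or a second reader for a later read, in a pilot study with no use for the outcome. The software argument needs a different tool in Aim 2, and nothing in the text says there is one.

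**Conclusion.** No change to the design or analysis follows. This is a gap that the study team can be expected to fill sensibly, together with a tension in wording. No effect on sensitivity, specificity or the sample size of 60 is shown, and no numerical size can be given, because the document contains no with/without-IRIS analysis.

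The conclusion rests on three assumptions:

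- the same attenuation algorithm serves Aims 1 and 2, as the text most naturally reads;
- the reads with and without IRIS remain an aid to interpretation and are not reported as a formal comparison, or the scan-review protocol that is not reproduced already sets their order;
- the reported accuracy is understood as that of VLE as used in the study, including any help IRIS gives in outlining areas.

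If the first failed, the transfer of the cut-off would need its own justification. If the second failed, the comparison would need a stated read order. The document gives no sign of either. The missing software name and version and the sentence on patient care are matters for editorial tidying and alter no planned result.

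### Aim 2 takes EMR depth as the superficial/deep reference without recording deep-margin status, so some correct deep VLE calls can count as false positives

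*Combined protocol and SAP*

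**What the plan says.** Section D.c.I (Aim 1), item b, defines histologic depth as the distance in microns "from mucosal surface to deepest point of invasion", measured on the EMR specimen. Its review items are: "EMR histology will be reviewed systematically to assess grade of tumor differentiation, depth of invasion, and presence or absence of lymphovascular invasion".

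Section D.c.II (Aim 2), item e, repeats the same three: "EMR specimens will be reviewed for grade of tumor differentiation, depth of invasion, and presence or absence of lymphovascular invasion". Deep-margin status is in neither list. Item e then states: "Depth of tumor invasion will be measured as outlined above and used to classify cancers as superficial vs. deep". Item f calculates sensitivity, specificity, both predictive values and accuracy for VLE "compared to histology as the gold-standard in staging T1 EAC", and adds kappa. No text flags, sets aside or reclassifies a specimen with an involved deep margin, and no other reference is named.

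Three other places bear on the point:

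- Section D.b reports from the group's earlier work that "evidence of lymphovascular invasion and deep margin involvement are significantly associated with reduced overall survival". Of these two features, only lymphovascular invasion reached the review lists.
- Section C says that VLE images "can reach an imaging depth of up to 3 mm". In Aim 2 the scan is done in the patient, before resection.
- The pitfalls section names one difficulty in measuring depth, duplicated muscularis mucosa, and answers it with two independent pathologists. It does not mention margin involvement.

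**The concern.** When tumour runs to the cut base of a specimen, the deepest point seen is where the tissue ends, not necessarily where the tumour ends. The true depth is at least the recorded depth. This matters for classification only if the recorded depth lies below the superficial/deep boundary and the true depth lies above it. The stated rule then treats the patient as definitely superficial.

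Two cells of the Aim 2 table are affected. If VLE correctly calls such a patient deep, the call is counted as a false positive. If VLE misses the deep disease, the miss is counted as a true negative. The depth error runs in one direction, so it does not average out, and a second pathologist cannot recover tissue that was not resected. Specificity is the quantity on which item f sizes the study. Without a margin field, the data cannot show whether the effect is negligible.

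**Working it through.** **Inputs.** From item f: 60 patients, about 75% T1a on histology, and target specificity 90%. Hence 60 × 0.75 = 45 recorded T1a and 15 recorded T1b. Assumed, because the documents do not give them: VLE sensitivity (Se) 90%, and q, the share of the 45 recorded-T1a patients whose disease is truly deeper.

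**The plan's own figure.** Item f states no interval width, so 60 cannot be confirmed independently. At 45 patients and specificity 0.90, the Wald half-width is 1.96 × √(0.90 × 0.10 / 45) = 0.0877, or 8.8 points (81.2% to 98.8%). It serves here only as a yardstick.

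**Apparent specificity.** With true specificity Sp,

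apparent specificity = (1 − q) × Sp + q × (1 − Se) = 0.90(1 − q) + 0.10q = 0.90 − 0.80q.

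| q | Truly deeper among 45 | Apparent specificity | Expected false positives | Of these, correct deep calls |
|---|---|---|---|---|
| 0% | 0 | 90.0% | 4.5 | 0 |
| 2% | 0.9 | 88.4% | 5.2 | 0.8 |
| 5% | 2.25 | 86.0% | 6.3 | 2.0 |
| 10% | 4.5 | 82.0% | 8.1 | 4.05 |

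Each such patient costs 0.80 / 45 = 1.78 points. The assumed sensitivity matters little. At q = 2%, 5% and 10%, Se = 80% gives 88.6%, 86.5% and 83.0%, and Se = 95% gives 88.3%, 85.75% and 81.5%.

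**Other measures, for two such patients.**

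- Recorded false positives: 43 × 0.10 + 2 × 0.90 = 6.1.
- Recorded true negatives: 45 − 6.1 = 38.9, of which 2 × 0.10 = 0.2 are missed deep cancers.
- True positives among the 15 recorded T1b: 15 × 0.90 = 13.5.
- Apparent accuracy: (13.5 + 38.9) / 60 = 87.3%, against a true 90%.
- Apparent PPV: 13.5 / (13.5 + 6.1) = 68.9%. Against the true class it is (13.5 + 1.8) / 19.6 = 78.1%.

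**If VLE does not respond to tumour below the resection plane.** Suppose that it calls these two patients deep only at the 10% false-positive rate. Apparent specificity then stays at 90%. Apparent sensitivity also stays at 13.5 / 15 = 90%, while sensitivity against true depth is (13.5 + 0.2) / 17 = 80.6%. The error is then hidden and flatters the test.

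**Cost of setting specimens aside.** Removing 2, 5 or 9 of the 45 leaves 43, 40 or 36. The same half-width formula then gives 9.0, 9.3 or 9.8 points instead of 8.8.

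**The case against.** The strongest reply is that few patients can be affected. On the T1a/T1b reading, which the specific aims and the sizing in item f adopt, tumour at a submucosal margin is already T1b and correctly classed. Misclassification needs an involved margin, a specimen that ends before tumour-bearing submucosa, and actual submucosal tumour left behind. So q can be no larger than the margin-positive rate among recorded T1a, and may be well below it. A reader might take the range for q as a margin-positive rate, but the documents supply neither figure. At 2% to 5% the shift is 1.6 to 4.0 points, under half the yardstick. This stands and limits the severity. The boundary itself is not wholly settled: Aim 1 item b also cites a 500 μm cut-off within the submucosa, under which a positive margin short of 500 μm could be misclassed too.

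Second, the 3 mm figure is a maximum, and the classifier is a signal-attenuation cut-off derived from excised specimens, not a reading of the tumour's lower edge. That VLE detects tumour beneath the resection plane is therefore an assumption. This also stands. If the assumption fails, the error takes the other form shown in the working.

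Third, the core-lab procedure, the standardised specimen review and Figure 3 cannot be seen and may record margins. That is possible. The plan's text would still contain no rule for using margin status in the analysis.

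A reader might also infer that truncated depths weaken the Aim 1 correlation, shift its cut-off, and call for censored regression. The documents do not support this. In Aim 1, VLE scans the same excised specimen that the pathologist measures, so both see tissue with the same base. Censored regression would target depth in the patient, which that scan does not show.

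**Conclusion.** The point holds for Aim 2 and is minor. Under the stated rule, a margin-positive specimen below the superficial/deep boundary is scored as definitely superficial although its depth is a lower bound. At 90% sensitivity and specificity, each truly deeper patient among the 45 costs about 1.8 points of apparent specificity: 88.4%, 86.0% and 82.0% at q = 2%, 5% and 10%. The size rests on an assumed q and on VLE responding to tumour that was not resected.

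It does not follow that every positive margin is a misclassification, that specificity will in fact fall by a given amount, or that the Aim 1 correlation is biased. The supportable conclusion is narrower: the plan neither lists the item needed to identify the affected specimens nor says how to analyse them.

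**What to change.** 1. Add deep-margin status to the histology review in Aim 1 item b and Aim 2 item e.
2. In Aim 2, define a margin-positive specimen with recorded depth below the boundary as indeterminate. State in the same sentence which boundary applies.
3. Report sensitivity, specificity, PPV, NPV and accuracy as planned, without the indeterminate specimens, and with all of them assigned to superficial and then all to deep. The all-superficial extreme coincides with the planned analysis, so this adds two sets of estimates.
4. Where routine care later yields resection pathology, report it as supportive only. It exists for selected patients and follows removal of tumour by EMR, so using it as the reference would apply different standards to different patients.
5. In Aim 1, flag margin-positive specimens and repeat the correlation and the cut-off derivation without them.

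The cost is one field on slides already under review, one sensitivity analysis in Aim 2 and one repeat analysis in Aim 1. A few patients may become indeterminate, with a slightly wider interval when they are left out. Patient management does not change.

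### Do the Aim 2 inclusion bullets let in patients without T1 EAC and so erode the planned 60?

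*Combined protocol and SAP*

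**What the plan says.** The protocol describes the Aim 2 population in several places in section D.c.II.

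- **Patient Selection, opening paragraph:** "Inclusion criteria include patients with T1 EAC who are undergoing endoscopic evaluation including EMR".
- **Inclusion bullets:** the disease criterion is "Patient undergoing an upper endoscopy with prior-biopsy confirmed" Barrett's esophagus. The other bullets cover age, consent and esophagitis. No exclusion bullet removes patients without cancer or without planned EMR.
- **Endoscopic Evaluation:** "If clinically indicated, an area(s) will be chosen for EMR".
- **Volumetric Laser Endomicroscopy:** the step again begins conditionally, "If an area(s) is chosen for EMR during" the endoscopic evaluation. For areas seen only on VLE, "All area(s) demarcated with VLE but not identified on endoscopic evaluation will undergo targeted biopsies".
- **Assessment of Cancer Depth of Invasion:** the algorithm is used to "measure degree of signal attenuation over areas demarcated for EMR". The EMR specimen supplies the reference depth, and what is classified as superficial or deep is the cancer.
- **Statistical Considerations and Data Analysis:** "60 patients with T1 EAC will need to be enrolled in this study", allowing that "approximately 75% of patients will be staged as having T1a disease on histology".

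Figure 4, the study flow diagram, is not shown in the text available for review.

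**The concern.** Someone screening from the bullets alone could enrol a Barrett's patient with no known cancer. The conditional EMR wording appears to expect such participants, since it would hardly be needed if EMR were a firm condition of entry. A patient without EMR-confirmed T1 EAC has no T1a or T1b reference result and adds nothing to sensitivity or specificity.

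The sample-size sentence speaks of enrolling 60, and enrolment comes before EMR histology. Its reference to histology attaches to the expected T1a share, not to the moment at which the 60 are counted. If the study stopped at 60 people entered on the bullets, specificity would rest on fewer than 45 T1a patients and sensitivity on fewer than 15 T1b patients, which is already a small number.

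**Working it through.** **1. The plan's own figure.** Inputs, from Statistical Considerations and Data Analysis: 60 patients with T1 EAC, 75% T1a, 90% specificity, 95% confidence. Tying specificity to the T1a share implies that T1b is the positive category.

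- T1a: 60 × 0.75 = 45
- T1b: 60 × 0.25 = 15
- Wald half-width for specificity: 1.96 × √(0.9 × 0.1 / 45) = 0.088, or 8.8 points

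The plan states no half-width or interval method, so 60 cannot be derived forwards. The 8.8 points is a back-calculation. The unstated width is a separate matter.

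**2. Do the two descriptions conflict?** Set side by side:

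| Source | Disease | Procedure |
|---|---|---|
| Opening paragraph | T1 EAC | evaluation that includes EMR |
| Bullets | biopsy-confirmed Barrett's | upper endoscopy |

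A patient with T1 EAC arising in biopsy-confirmed Barrett's and coming to EMR meets every line. The opening sentence presents itself as part of the inclusion criteria, and nothing says the bullets supersede it. Aim 2 in section B, the Aim 2 heading and the sample-size sentence all name T1 EAC. Reading the two cumulatively is therefore natural, although the text does not spell it out.

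**3. Who reaches the accuracy table?** Each patient needs two results.

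- *Index result:* attenuation is read only over areas marked for EMR. With no EMR area there is no index result.
- *Reference result:* depth comes from the EMR specimen, and the units classified are cancers. With no cancer in the specimen there is no invasion depth and no stage.

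A patient without EMR, or whose EMR shows no cancer, has no cell in the two-by-two table. Counting such a patient as superficial would depart from the plan, which evaluates VLE in staging T1 EAC. The rule that sends VLE-only areas to biopsy concerns extra areas. A patient with such an area can still have EMR elsewhere, so the rule does not decide who enters.

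**4. What if accrual were counted at entry?** The documents give no yield *f* of EMR-confirmed T1 EAC among those enrolled, so the values below are assumptions. T1a = 60 × *f* × 0.75; T1b = 60 × *f* × 0.25; half-width = 1.96 × √(0.09 / T1a).

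| Assumed *f* | T1a / T1b | Half-width, points |
|---|---|---|
| 1 | 45 / 15 | 8.8 |
| 0.75 | 33.8 / 11.3 | 10.1 |
| 0.5 | 22.5 / 7.5 | 12.4 |
| 0.3 | 13.5 / 4.5 | 16.0 |

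The first row is what the sample-size sentence says. The others require counting people whom that sentence does not count. The Aim 1 database, with 60 T1 EAC specimens among over 200 EMR specimens, does not supply *f*: it counts retrospective specimens, not Aim 2 enrolments.

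**The case for a change.** The strongest argument is that the conditional EMR wording appears twice and fits the broader bullets better than the narrow opening sentence. The opening paragraph itself begins with referrals for Barrett's and early neoplasia, which is wider than T1 EAC. Stage is set by EMR after enrolment, so even a careful site will enrol some patients who prove not to have T1 EAC. In an accuracy study the denominator should be fixed beforehand, and a sentence or two would do it.

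Much of this stands as description. The bullets do omit the criterion, some enrolled patients may have no EMR histology, and no visible text says when the 60 are counted or how unevaluable scans are treated. It does not follow that the result is at risk. Conditional EMR leaves resection to clinical judgement; it does not create a second target population. The denominator is not open in the way feared, because the measurement and reference rules already confine it to EMR-confirmed cancers. Unevaluable scans are a reporting question separate from eligibility, and the documents give no rate from which to size their effect. Figure 4 may also show the flow, so the absence of a statement in the visible text is weak evidence.

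**Conclusion.** The omission in the bullets is real, but it is a drafting gap and calls for no change to the plan. Followed as written, the study aims for 60 patients with T1 EAC, about 45 T1a and 15 T1b, and the loss of precision from this point is zero. The wider intervals in the table arise only if accrual is counted against the plan's own sentence, and then only to an extent set by a yield that the documents do not give.

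This rests on three readings: that the opening sentence and the bullets apply together, that the 60 means patients with T1 EAC, and that the accuracy table contains only cancers with EMR depth. The text supports each. An analyst would ordinarily count confirmed cases towards the 60 and report other enrolled patients outside the accuracy calculation. Repeating the criterion in the list would be tidier, but would alter neither the target nor the analysis.
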